**5. Population-level summary for the variables:**

Difference in mean change in the monthly average number of migraine days from the 28-day baseline period during the 12-week between fremanezumab and placebo.

## 2. STUDY DESIGN

### 2.1. General Design

This is an approximately 28-week, multicenter, randomized, double-blind, placebo investigational medicinal product (IMP)-controlled, parallel-group study to evaluate the efficacy and safety of fremanezumab self-administered at monthly doses of 225 mg sc and a quarterly dose of 675 mg sc (ie, one dose using 3 prefilled syringes with 225 mg each) in adult patients with migraine and MDD. The study will consist of a 28-day (ie, 4-week) baseline period, a 12-week double-blind treatment phase followed by a 12-week open-label extension phase, and an end-of-treatment visit (approximately 12 weeks after the final dose of study drug).

The total duration of patient participation in the study is planned to be approximately 28 weeks. Patients are expected to complete the entire duration of the study.

Patients who fulfill the criteria for migraine will be further delineated as patients with chronic migraine (CM) or episodic migraine (EM), for stratification and other analyses.

CM is defined as:

Patient fulfills the following criteria for CM in prospectively collected baseline information during the 28-day baseline period:

- headache occurring on  $\geq 15$  days
- on  $\geq 8$  days, fulfilling any 1 of the following:
  - ICHD-3 diagnostic criteria C and D for 1.1 Migraine without aura (Appendix I of the study protocol)
  - ICHD-3 criteria B and C for 1.2 Migraine with aura (Appendix I of the study protocol)
  - probable migraine (a migraine subtype where only 1 migraine criterion is missing)
  - triptan or ergot derivative used to treat established headache.

EM is defined as:

The patient fulfills the following criteria for EM in prospectively collected baseline information during the 28-day baseline period:

- headache occurring  $\geq 4$  days but  $< 15$
- on  $\geq 4$  days, fulfilling any 1 of the following:
  - ICHD-3 diagnostic criteria C and D for 1.1 Migraine without aura (Appendix I of the study protocol)
  - ICHD-3 criteria B and C for 1.2 Migraine with aura (Appendix I of the study protocol)

- probable migraine (a migraine subtype where only 1 migraine criterion is missing)
- triptan or ergot derivative used to treat an established headache

At the randomization visit (day 1), patients will be randomly assigned to 1 of 2 treatment groups of 225 mg sc fremanezumab or placebo in a 1:1 ratio. Patients will receive their assigned study treatment on visit 2 (day 1), visit 3 (day 29), and visit 4 (day 57) and then continue into the open-label extension phase in which all patients will receive a quarterly dose of 675 mg sc fremanezumab on visit 5 (day 85). Investigators can contact patients in between study visits per their clinical judgment.

Patients who complete all scheduled visits will have procedures and assessments performed at visit 6 (end of treatment [EOT]). Patients who withdraw from the study before completing the 24-week treatment phase will have visit 6 (EOT) procedures and assessments performed at their final visit. The end of study is defined as the last visit (end-of-treatment/early withdrawal visit [visit 6]) of the last patient.

Study procedures and assessments with their timing are summarized in Table 4 of the study protocol.

## 2.2. Randomization and Blinding

After the 28-day baseline period, the first 12 weeks of this study will be double-blind. Patients and investigators will remain blinded to IMP assignment during this part of the study. This will be followed by a 12-week open-label extension phase.

Patients will receive 225 mg sc fremanezumab (visit 2, visit 3, and visit 4) or matching placebo (visit 2) in monthly doses.

For the first phase of this study, the sponsor, investigators, study staff, and patients will be blinded to treatment assignment. A computer-generated master randomization list will be provided to drug packaging facilities. The packaging vendor(s) will package active drug and placebo into single-visit kits according to Good Manufacturing Practice procedures. Kits will be identical in appearance and contain 1 prefilled syringe with either active drug or placebo.

Patients will be stratified based on sex, country, migraine classification (ie, CM or EM), and PHQ-9 score category (10 to 14, 15 to 19, and  $\geq 20$ ) to ensure balance for the covariates.

Patients will be randomly assigned to treatment groups by means of a computer-generated randomization list using electronic interactive response technology (IRT). This system is used to ensure a balance across treatment groups. The specifications for randomization will be under the responsibility and oversight of Teva Global Statistics.

At randomization visit (day 1), each patient will be randomized in a 1:1 ratio within the stratum to which he or she belongs to receive monthly 225 mg sc fremanezumab or placebo, as assigned by the IRT. In the open-label extension phase starting at week 12, however, all patients will receive active treatment with a quarterly dose of 675 mg sc fremanezumab.

## 2.3. Data Monitoring Committee

There will be no Data and Safety Monitoring Board in this study.

## **2.4. Sample Size and Power Considerations**

A sample size of 288 (144 per treatment group) evaluable patients completing the study will provide 90% power to detect a treatment difference of 2 days with a common standard deviation of 5.2 days in changes from the 28-day baseline period in monthly average migraine days between active and placebo groups at a 2-sided alpha level of 0.05. This sample size will provide approximately 80% power to detect a treatment difference of 2 points with a common standard deviation of 6 points in the change from randomization visit (day 1) in HAM-D 17 total score at a 2-sided alpha level of 0.05. Assuming a 15% drop-out rate, approximately 340 patients (approximately 170 patients per treatment group) will be randomized.

## **2.5. Sequence of Planned Analyses**

### **2.5.1. Planned Interim Analyses**

No interim analysis is planned for this study.

### **2.5.2. Final Analyses and Reporting**

All analyses identified in this SAP will be performed after the final database lock.

### **3. ANALYSIS SETS**

#### **3.1.1. Intent-to-Treat Analysis Set**

The intent-to-treat (ITT) analysis set will include all randomized patients.

In the ITT analysis set, treatment will be assigned based on the treatment to which patients were randomized, regardless of which treatment they actually received.

#### **3.1.2. Modified Intent-to-Treat Analysis Sets**

The double-blind modified intent-to-treat (mITT) analysis set is a subset of the ITT analysis set including only patients who receive at least 1 dose of IMP and have at least 10 days of postrandomization efficacy assessment on the primary endpoint. The open-label mITT analysis set is a subset of the ITT analysis set including only patients who receive at least 1 dose of IMP during the open-label treatment period and have at least 10 days of diary entries during the open-label period.

In the double-blind mITT analysis set, treatment will be assigned based on the treatment to which patients were randomized, regardless of which treatment they actually received.

#### **3.1.3. Safety Analysis Sets**

The double-blind safety analysis set will include all randomized patients who receive at least 1 dose of IMP during the double-blind treatment period. The open-label safety analysis set will include all patients who receive at least 1 of dose of IMP during the open-label treatment period.

In the double-blind safety analysis set, treatment will be assigned based on the treatment patients actually received, regardless of the treatment to which they were randomized, unless otherwise specified.

Patients who begin prohibited therapies during the study will be included in the safety analysis sets but not the per-protocol (PP) analysis set (Section 3.1.4).

#### **3.1.4. Per-Protocol Analysis Set**

The PP analysis set is a subset of the mITT analysis set including only patients without important protocol deviations during the double-blind treatment period, including any deviation of the inclusion/exclusion criteria or any deviations or omissions of the IMP administration. Patients with less than 75% diary compliance during the double-blind treatment period will be excluded from the PP analysis set. A blinded data review meeting will be conducted prior to the database lock in order to determine the exclusion of the patients from the PP analysis set. After database lock and unblinding, patients who received study drug different from the study drug they were randomized to will also be excluded from the PP analysis set.

## 4. GENERAL ISSUES FOR DATA ANALYSIS

### 4.1. General

Descriptive statistics for continuous variables include n, mean, standard deviation (SD), standard error (SE), median, minimum, and maximum. Descriptive statistics for categorical variables include patient counts and percentages, missing category will be displayed as appropriate.

### 4.2. Specification of Baseline Values

For migraine days, the baseline value is the total number of migraine days during the 28-day baseline period. If the baseline period is greater or less than 28 days, the baseline value will be normalized to 28 days. In addition, if the baseline period is 28 days but there are days with missing diary, the baseline value will be normalized to 28 days.

For all other assessments, the baseline value is the last observed data prior to the first dose of study drug.

### 4.3. Handling Withdrawals and Missing Data

If a patient has  $\geq 10$  days of electronic headache diary data after 1st dose of the study drug, his/her monthly average number of migraine days *during the 12-week period* or monthly number of migraine days *during the 4-week period* will be prorated to 28 days.

Multiple imputation (MI) method will be applied on the primary variable as sensitivity analyses. The methods will be described in detail in Section 6.2.3.

A patient's monthly number of migraine days *during the 4-week period* after each dose of study drug will be calculated for months 1, 2, 3, and 6. If a patient has missing diary days when calculating the monthly number of migraine days, the following method will be used to handle the missing data.

- If a patient has  $\geq 10$  days of electronic headache diary data for a month, the monthly number of migraine days will be prorated to 28 days for that month.
- If a patient has  $< 10$  days of electronic headache diary data for a month, the monthly number of migraine days will be considered as missing.

For the HAM-D, HAM-A and HIT-6, if 1 or more items are missing then the total score is missing. The missing questionnaire items handling for the MSQOL questionnaire is discussed in [Appendix E](#).

### 4.4. Study Days and Visits

Study days are numbered relative to the 1st day of study drug administration. The start of treatment (day 1) is defined as the date on which a patient takes the 1st dose of study drug, as recorded on the study drug administration case report form (CRF). Days will be numbered relative to treatment start (ie, ..., -2, -1, 1, 2, ...; with day 1 being the 1st day of study drug administration and day -1 being the day before the 1st day of study drug administration).

The 4-week (28-day) visit windows for the electronic headache diary based efficacy endpoints will be determined based on the actual dosing day. The run-in phase is defined as day -28 to -1 before the 1st injection on day 1. Treatment phase including month 1, 2, 3, and 6 is from the beginning of the 1st injection of study drug to visit 6/day 169 or the EOT visit. The monthly visit windows are separated by each dosing date/time. Month 1 is from the date/time of the 1st dose of study drug administration on day 1 to the date/time just before the 2nd dose. Month 2 is from the date/time of the 2nd dose to the date/time just before the 3rd dose. Month 3 is from the date/time of the 3rd dose to the date/time just before the 4th dose. Month 6 is from 57 days after the date/time of the 4th dose to the EOT on day 169 approximately.

Throughout this document, all by month efficacy summaries for the headache data will refer to these visit windows.

For all other by-visit summaries, if there are multiple assessments at a postbaseline visit then the last non-missing assessment at that visit will be used for the summary. This includes assessments at the scheduled and unscheduled visits.

For patients who withdraw from the study, their efficacy and safety data at the early termination visit will be excluded from the by-visit summaries but will be included in the last assessment summaries.

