#### **6.3.1.2. Analysis**

The HAM-D 17 total score change from baseline to week 8 will be analyzed using the same MMRM method as described in section 6.2.3.1. The analysis will also be done at weeks 4 and 12.

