#### **6.3.3.2. Analysis**

The MSQOL domains (Role Function-Restrictive, Role Function-Preventive, and Emotional Function) scores change from baseline to week 12 will be analyzed using the same MMRM method as described in section [6.2.3.1](#). The analysis will also be done at weeks 4 and 8.

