#### **6.3.4.2. Analysis**

The CGI-S rating change from baseline to weeks 4, 8, and 12 will be analyzed using the same MMRM method as described in section [6.2.3.1](#).

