#### **6.3.5.2. Analysis**

The HIT-6 disability score change from baseline to week 12 will be analyzed using the same MMRM method as described in section 6.2.3.1. The analysis will also be done at weeks 4 and 8.

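### As written, the SAP gives early-termination HAM-D 17, CGI-S, MSQoL and HIT-6 scores no route into the secondary MMRMs, including the key secondary test

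*SAP*

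**What the plan says.** SAP 4.4 states, for patients who withdraw, that "their efficacy and safety data at the early termination visit will be excluded from the by-visit summaries". The sentence goes on: "but will be included in the last assessment summaries".

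The scores exist. Under SAP 2.1, patients who withdraw before the end of the 24 weeks "will have visit 6 (EOT) procedures and assessments performed at their final visit". Protocol Appendix B, item 6, lists HAM-D 17, CGI-S, MSQoL and HIT-6 among the early-termination procedures.

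All four scales are tested by a repeated-measures model at weeks 4, 8 and 12:
- HAM-D 17 (SAP 6.3.1.2, key secondary): "The HAM-D 17 total score change from baseline to week 8 will be analyzed using the same MMRM method", with weeks 4 and 12 also analysed.
- MSQoL (SAP 6.3.3.2): "scores change from baseline to week 12 will be analyzed using the same MMRM method", also at weeks 4 and 8.
- CGI-S (SAP 6.3.4.2): "The CGI-S rating change from baseline to weeks 4, 8, and 12 will be analyzed using the same" model.
- HIT-6 (SAP 6.3.5.2): "The HIT-6 disability score change from baseline to week 12 will be analyzed using the same MMRM method", also at weeks 4 and 8.

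SAP 4.3 applies multiple imputation to the primary variable only. SAP 7 places HAM-D 17 second in the fixed testing sequence.

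**The concern.** An ET score is the observation closest to the decision to leave. If patients leave because depression or headache impact is worsening, that score may be the only record of it. The MMRM is valid if missingness depends only on data in the model. Leaving out the last score collected makes that assumption harder to defend.

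The issue weighs most on HAM-D 17 at week 8. That test is confirmatory, and nothing in the SAP examines how sensitive it is to missing data. The per-protocol repeat in SAP 6.1 changes the population but does not address missingness. The primary endpoint is not affected, because it is built from diary days.

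**Working it through.** **1. Can an ET score enter the MMRM?**
- The model in SAP 6.2.3.1 has a scheduled time point as its repeated factor, so each score needs a week label.
- The one rule on ET data (SAP 4.4) withholds it from by-visit summaries. The dosing-date windows in the same section cover diary endpoints only.
- The alternative use, a last-assessment summary, has no visible efficacy counterpart. SAP 6.1 describes efficacy summaries by month or week and over 12 weeks. A last on-study assessment appears only in the safety sections (SAP 8.5 to 8.8).
- So no visible text gives an ET questionnaire score a week, and exclusion is the natural programming result. The exploratory-endpoint text is redacted, and SAP Appendix B (endpoint derivation) is not in the available text; neither is counted as missing.

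**2. Who contributes nothing?**
The double-blind mITT set (SAP 3.1.2) needs one dose and 10 days of post-randomization efficacy data. A patient who leaves on day 20 can qualify and have an ET HAM-D 17, yet have no scheduled post-baseline HAM-D 17.

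**3. The plan's own figures (SAP 2.4)**
Inputs: 144 per group, two-sided alpha 0.05, HAM-D 17 difference 2 and SD 6, primary difference 2 and SD 5.2, drop-out 15%.

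Power = Φ(δ / (SD × √(2/n)) − 1.96)
- HAM-D 17: 2 / (6 × √(2/144)) = 2.828; Φ(0.868) = 80.7%, against about 80% stated.
- Primary, same formula with SD 5.2: 90.4%, against 90% stated.
- Randomized: 288 / 0.85 = 339, against about 340 stated.

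All three reproduce.

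**4. How many week-8 scores?**
Assumption A: 5-10% of the 340 leave before week 8, so 17 to 34 patients.

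Assumption B: a quarter to a half of their ET visits fall nearest week 8. The lower value follows from exits spread evenly over days 1-56, with days 43-56 nearest week 8: 14/56 = 25%. The upper value allows exits to cluster later.
- Low: 17 × 0.25 ≈ 4.
- High: 34 × 0.5 = 17.

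**5. What is that worth in power?**
Same formula, HAM-D 17, n per group rounded down. It assumes that everyone still in the study has a week-8 score and that a mapped score carries full information.

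| Leave before week 8 | n and power, unmapped | Add a quarter | Add a half |
|---|---|---|---|
| 10% (306 remain) | 153: 83.0% | 157: 84.0% | 161: 84.9% |
| 5% (323 remain) | 161: 84.9% | 163: between 84.9% and 85.7% | 165: 85.7% |

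The outer bounds are 80.7% (144 per group, no leaver scores) and 86.7% (170 per group, every leaver's score usable at week 8). The upper bound could not be reached with windows of this kind. The realistic gain is at most about two percentage points, and less in an MMRM, which already draws on leavers' earlier scores.

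**The case against.** **The rule concerns summaries, not model input.** This stands as a point of wording. A reader might infer that the SAP expressly bars ET scores from the MMRM; it does not. The exclusion follows because no week label is supplied. If the sponsor intends these scores to be used, the SAP still has to say where they go.

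**The scores are not thrown away.** A reader might infer that they are. The second half of the SAP 4.4 sentence keeps them for last-assessment summaries, and scores from earlier scheduled visits remain in the model. What can be said is that the ET score itself plays no visible part in an efficacy test.

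**Leaving off-schedule scores out of an MMRM is defensible.** This has force. Mapping a day-43 score to week 8 mixes exposure times, and an ET score may follow the end of treatment. The hypothetical strategies in SAP 1.3 cover such events, but only for the primary estimand. Protocol section 6 also bars analysis of efficacy assessments done after the specified time, and scheduled visits have windows of ±3 days. An ET assessment is itself a protocol procedure, so that text does not clearly exclude it, but the SAP should settle the matter. These are reasons to report both versions rather than to leave the rule unstated.

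**Is SAP 4.4 inconsistent in keeping unscheduled scores?** A reader might think so. The unscheduled-visit sentence is a tie-break for several assessments at one visit, and Protocol Appendix B, item 7, does not list these scales for unscheduled visits. The argument does not hold.

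**Conclusion.** The point holds as a gap in a stated rule. Followed as written, the plan most naturally leaves the ET scores of double-blind leavers out of all four scale-based secondary analyses. The key secondary then rests on an untested missing-at-random assumption.

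The size is modest: roughly 4 to 17 week-8 HAM-D 17 scores, resting on the two assumptions about when patients leave. The documents give no withdrawal timing that would narrow this.

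Two larger readings are not supported. A reader might take 15% of 340, or 51 patients, as the number affected. That rate refers to completing the whole study, so it includes open-label leavers, who would normally already have their week 4, 8 and 12 scores, and patients lost to follow-up, who may have no ET visit. A reader might also infer a power shortfall. There is none, because planned HAM-D 17 power counts completers only. Possible bias is the stronger reason to act, and its direction and size cannot be computed from the documents.

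**What to change.** Before database lock and unblinding, amend SAP 4.4 and 6.3:

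1. State that double-blind ET questionnaire scores enter the MMRM at the nearest scheduled week, by a fixed window, when that week has no scheduled value. For example: days 15-42 = week 4, days 43-70 = week 8, day 71 to before the open-label dose = week 12.
2. Never use a score taken after the open-label dose for these weeks.
3. Report the HAM-D 17 MMRM without mapped scores as a sensitivity analysis, or the reverse, and name which one is confirmatory.
4. Name the efficacy last-assessment summary that SAP 4.4 refers to, or limit that phrase to safety. Add a line reconciling the mapping with Protocol section 6.

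The cost is SAP wording, one derivation step and one extra model run, with no new data collection. The downside is timing: a mapped score can lie up to 14 days from its nominal day (day 43 against day 57). A patient who leaves before day 15 would still contribute no post-baseline score.

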#### 4.5. Region of Pooled Countries

The countries will be pooled to 3 regions as presented in [Table 2](#) for the analysis.

**Table 2: The Region of Pooled Countries**

Region	Country
United States	United States
Europe	Czech Republic, Finland, France, Germany, Greece, Italy, Poland, Spain, United Kingdom
Rest of World	Israel, Russia, Ukraine

## **5. STUDY POPULATION**

### **5.1. General**

The ITT analysis set will be used for all study population summaries unless otherwise specified. Summaries will be presented by treatment group and for all patients (ie, total).

### **5.2. Patient Disposition**

Patients screened, patients screened but not randomized, and the reasons the patients were not randomized will be summarized only for the total group using patient counts.

Patients in the ITT analysis set, ITT analysis set but not treated, double-blind safety analysis set, double-blind mITT analysis set, double-blind mITT analysis set but not PP analysis set (with reason not in the PP set), and PP analysis set, patients who complete and withdraw from the double-blind treatment period, patients in the open-label safety analysis set and open-label mITT analysis set, and patients who complete and withdraw from the study will be summarized using descriptive statistics. Patients who withdraw from double-blind treatment and patients who withdraw from the study will also be summarized using descriptive statistics by reason for withdrawal. The denominator for calculating the percentages will be the number of patients in the ITT analysis set.

### **5.3. Demographics and Baseline Characteristics**

The continuous variables of patient age, weight, height, and body mass index (BMI), and time since initial migraine diagnosis (years) will be summarized using descriptive statistics. The categorical variables of patient sex, race, ethnicity, migraine classification, country, region, PHQ-9 score category, patient sex as randomized, migraine classification as randomized, and PHQ-9 score category as randomized will be summarized using descriptive statistics for each category. Missing categories will be presented if necessary.

This summary will also be done for the open-label safety analysis set.

The baseline total number of migraine days, HAM-D 17 total score, MSQOL domain scores, CGI-S rating, HIT-6 disability score, PHQ-9 total score, HAM-A total score, and WPAI domain scores will be summarized using descriptive statistics.

